### ***Change in study treatment after the occurrence of very low LDL-C level***

For each definition of very low LDL-C level, the following statistics will be calculated:

- Among the patients who had a very low LDL-C level and received a dose of alirocumab at 150 mg at the time of the corresponding LDL-C test:
  - Number and percentage of patients for whom the dose of alirocumab was changed to 75 mg, at least once at any time after the first occurrence of a very low LDL-C level,
  - Number and percentage of patients for whom alirocumab was discontinued at any time after the first occurrence of a very low LDL-C level,
  - Number and percentage of patients for whom the doses of other lipid-lowering drugs were decreased at any time after the first occurrence of a very low LDL-C level,
  - Number and percentage of patients for whom other lipid-lowering drugs were discontinued at any time after the first occurrence of a very low LDL-C level.
- Among the patients who have a very low LDL-C level and received a dose of alirocumab at 75 mg at the time of the corresponding LDL-C test:
  - Number and percentage of patients for whom alirocumab was discontinued at any time after the first occurrence of a very low LDL-C level,
  - Number and percentage of patients for whom the doses of other lipid-lowering drugs were decreased at any time after the first occurrence of a very low LDL-C level,
  - Number and percentage of patients for whom other lipid-lowering drugs were discontinued at any time after the first occurrence of a very low LDL-C level.

For patients who experienced a very low LDL-C several times during the observational period, only the first occurrence will be considered.

The 95% CI will be provided. In case of a number of patients deemed insufficient, the Clopper-Pearson algorithm will be used to compute the 95% CI.

### ***Discontinuation of alirocumab***

The following statistics will be calculated:

- Number and percentage of patients for whom alirocumab is discontinued during the observational period
  - Overall,
  - By starting dose of alirocumab.
- Among the patients for whom alirocumab is discontinued
  - Number and percentage of patients on each dose (75 versus 150 mg) prior to discontinuation,
  - Number and percentage of patients who had LDL-C <25 mg/dL (0.65 mmol/L) and <15 mg/dL (0.39 mmol/L) prior to discontinuation, respectively,

- Number and percentage of patients according to each reason for discontinuation, if available,
- Number and percentage of patients who restarted alirocumab in the observational period.

For patients who discontinued alirocumab several times during the observational period, only the first occurrence will be considered.

The 95% CI will be provided. In case of a number of patients deemed insufficient, the Clopper-Pearson algorithm will be used to compute the 95% CI.

In addition, a listing with all patients who experienced at least once a very low LDL-C level during the observational period will be provided with the following parameters: country, date of enrollment, starting dose of alirocumab, LDL-C level at inclusion, LDL-C <25 mg/dL (Y/N), LDL-C <15 mg/dL (Y/N), date corresponding to the lipid test, down-titration (Y/N), date of down-titration, up-titration (Y/N), date of up-titration, discontinuation of alirocumab (Y/N), date of discontinuation.

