## 2.2 DISPOSITION OF PATIENTS

This section describes patient disposition for both patient study status and the patient analysis populations.

- Screened patients are defined as any patient who signed the informed consent.
- Enrolled patients consist of all screened patients, with a treatment kit number allocated and recorded in the interactive voice response system (IVRS)/interactive web response system (IWRS) database, regardless of whether treatment kit was used or not.

For patient study status, the total number of patients in each of the following categories will be presented in the clinical study report using a flowchart diagram or summary table:

- Screened patients.
- Screen failure patients and reasons for screen failure.
- Enrolled patients.
- Enrolled but not treated patients and reason for not being treated.
- Enrolled and treated patients.
- Patients who did not complete the study treatment period as per protocol.
- Patients who discontinued the study treatment by main reason for permanent treatment discontinuation.
- Status at last study contact.

For all categories of patients (except for the screened categories) percentages will be calculated using the number of enrolled patients as the denominator. A listing of other reasons for treatment discontinuation will be provided.

The incidence of premature treatment discontinuation (irrespective of the reason) and premature treatment discontinuation due to AEs will be presented graphically, using Kaplan-Meier method (provided that the number of patients concerned is not too small).

The disposition of patients will be presented overall and by country or pooled countries.

A patient is considered **lost to follow-up** (LTFU) if the patient has the information box “*Lost to Follow-Up*” ticked in the CRF p.46.

**All critical or major deviations** potentially impacting efficacy analyses, enrollment, and drug-dispensing irregularities, and other major or critical deviations will be summarized in tables giving numbers and percentages of deviations. The deviations are listed in the data review and surveillance plan.

In addition, the following populations will be summarized overall:

- Modified intent-to-treat population (mITT).
- Safety population.
- Self-injection population: safety population patients who gave themselves at least 1 alirocumab injection during the observational period.

Definition of the study population are given in [Section 2.3](#).

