## 2.3 ANALYSIS POPULATIONS

### 2.3.1 Efficacy population

The efficacy population considered for efficacy analyses will be the mITT population.

The modified intent-to-treat population (mITT) also referred as on-treatment in section above, is defined as: all enrolled patients who took at least one dose or part of a dose of alirocumab and had an evaluable efficacy endpoint during the efficacy treatment period. The main efficacy endpoint will be evaluable provided that the 2 following conditions are met:

- Availability of a baseline calculated LDL-C value (last value available prior to the first injection of alirocumab).
- Availability of the calculated LDL-C within the analysis window associated to Week 12.

The efficacy treatment period is defined as the time period from the first injection of alirocumab up to the day of last injection + 21 days.

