#### **2.4.4.4 Additional efficacy analyses**

##### ***Occurrence of very low LDL-C level***

A LDL-C level <25 mg/dL (0.65 mmol/L) will be defined as very low. An alternative definition with a cut-off at 15 mg/dL (0.39 mmol/L) will also be used.

For each definition of very low LDL-C level, the number and percentage of patients who had a very low LDL-C level at least once during the observational period will be provided overall, by the LDL-C level at baseline (<70 mg/dL (1.81 mmol/L),  $\geq 70$  mg/dL and <100 mg/dL (2.59 mmol/L),  $\geq 100$  mg/dL and <130 mg/dL (3.37 mmol/L),  $\geq 130$  mg/dL and <160 mg/dL (4.14 mmol/L),  $\geq 160$  mg/dL) and by starting dose of alirocumab.

Among patients with a very low LDL-C level, the number and percentage of patients receiving each level of dose for alirocumab (75 mg and 150 mg) at the time of the corresponding LDL-C test will be provided. The time from the first injection of Alirocumab to the first occurrence of a very low value of LDL-C will also be displayed.

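### SAP 2.4.4.4 names no population, so its discontinuation, very-low-LDL-C and statin-change tables default to mITT and leave out patients who stop permanently before Day 50

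*SAP*

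**What the plan says.** SAP 2.4.4.4 carries the heading "Additional efficacy analyses" and belongs to SAP 2.4.4 on efficacy endpoints. It covers four topics: occurrence of very low LDL-C (below 25 and below 15 mg/dL), treatment changes afterwards, discontinuation of alirocumab, and statin dose reduction or discontinuation. The discontinuation part asks for the "Number and percentage of patients for whom alirocumab is discontinued during the observational period", overall and by starting dose. Among those who stop, it asks for dose before stopping, LDL-C below 25 or 15 mg/dL before stopping, reason, and restarts. None of the four parts names a population.

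SAP 2.3.1 supplies the default: "The efficacy population considered for efficacy analyses will be the mITT population". That set is described as "The modified intent-to-treat population (mITT) also referred as on-treatment in section above". Its members must have "had an evaluable efficacy endpoint during the efficacy treatment period", and one condition is "Availability of the calculated LDL-C within the analysis window associated to Week 12". The efficacy treatment period runs "up to the day of last injection + 21 days".

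Discontinuation also appears in SAP 2.2. There, permanent stops are tabulated by main reason over all enrolled patients, and "The incidence of premature treatment discontinuation (irrespective of the reason) and premature treatment discontinuation due to AEs will be presented graphically".

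**The concern.** How many patients stop the drug, on which dose and for what reason is a question about everyone treated. A population that requires patients to be on drug near Week 12 selects on the outcome being counted, because early permanent stoppers leave both numerator and denominator.

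Several of these summaries are planned nowhere else: discontinuation by starting dose, by dose at stopping and by preceding LDL-C; what was done after a very low LDL-C; and statin changes by alirocumab dose. SAP 1.5 says the very-low-LDL-C analyses were added to characterise these cases better. Protocol Section 4 says the safety of such values is still being assessed, and Protocol 8.1 says the maximum LDL-C reduction is usually reached by Week 4. A patient with a very low value at Week 4 or 8 who then stops for good is of direct interest, and mITT drops that patient from the tables.

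**Working it through.** The plan gives no expected discontinuation figure to reproduce. Its only precision figures are the intervals for adverse event rates at N = 1300 (SAP 1.3). They reproduce: at 10%, 1.96 × √(0.10 × 0.90 / 1300) = 1.6 points, giving 8.4% to 11.6%. That half-width serves as a yardstick below.

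**Which population applies**
- SAP 2.4.2 (medications), 2.4.3 (exposure and compliance) and 2.4.5 (safety) each name the safety population.
- SAP 2.4.4.2 names mITT for efficacy variables and also holds the titration patterns, which SAP 2.1.3.2 labels as on-treatment.
- SAP 2.4.4.4 is silent. Its heading and SAP 2.3.1 together give mITT.

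**Earliest qualifying last injection**
- The Week 12 window is Days 71 to 98, with the first injection on Day 1 (SAP 2.5.4, Table 3).
- The LDL-C must fall on or before last injection + 21 days (SAP 2.3.1).
- So last injection + 21 ≥ 71, that is, last injection ≥ Day 50.

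On an exact two-weekly schedule:

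| Last injection (day) | Efficacy period ends (day) | Can reach Day 71? |
|---|---|---|
| 1 | 22 | No |
| 15 | 36 | No |
| 29 | 50 | No |
| 43 | 64 | No |
| 57 | 78 | Yes |

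A fourth injection given 7 days late, on Day 50, just reaches Day 71.

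**Comparison with the protocol's mITT**
Protocol 11.3.1.1 accepts an LDL-C in any window up to Week 12. The Week 4 window opens on Day 15, so even a single Day 1 injection (period ending Day 22) could qualify. That version would keep more early stoppers, but still not those without an on-treatment sample.

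**Size, by illustration**
Let D be the share of treated patients who discontinue and e the share whose last injection is before Day 50. If every other patient has a Week 12 LDL-C, the mITT table shows (D - e) / (1 - e).

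| D | e = 1% | e = 2% | e = 3% | e = 5% |
|---|---|---|---|---|
| 10% | 9.1% | 8.2% | 7.2% | 5.3% |
| 15% | 14.1% | 13.3% | 12.4% | 10.5% |
| 20% | 19.2% | 18.4% | 17.5% | 15.8% |

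For example, (0.10 - 0.02) / 0.98 = 8.2% and (0.10 - 0.05) / 0.95 = 5.3%. At D = 10% and e = 2% the shift is 10 - 8.2 = 1.8 points, slightly more than the 1.6-point half-width above.

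If a further 5% of patients continue on drug but lack a Week 12 LDL-C, the D = 10% results become 0.08 / 0.93 = 8.6% and 0.05 / 0.90 = 5.6%. Missing samples in continuing patients therefore offset part of the shift.

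**The case against.** The strongest reply is that SAP 2.4.4.4 never says mITT. The explicit mITT sentence in SAP 2.4.4.2 concerns efficacy variables, and stopping a drug or lowering a statin dose is hardly one. SAP 2.4.4.4 speaks of the observational period, which SAP 2.2 uses for a safety-population subset and SAP 2.1.3.2 uses alongside the on-treatment label, so the term settles nothing. This stands in part: mITT applies by default, not by express assignment. If it was not intended, the tables have no stated population, and the same sentence is needed.

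The second reply is that early stops are reported elsewhere, and this also stands. SAP 2.2 covers permanent stops over all enrolled patients. SAP 2.4.5.1 covers adverse events leading to discontinuation, and SAP 2.4.3.2 temporary discontinuations, both in the safety population. SAP 2.4.4.4 also plans a listing of all patients with a very low LDL-C, with discontinuation dates, and nothing in its wording limits it to mITT. A reader might infer that early discontinuers vanish from the report; they do not. What these other outputs lack is the set of breakdowns planned only in 2.4.4.4.

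A reader might also infer that nobody who stopped before Day 50 can be counted. That is true only of permanent stops. The discontinuation part provides for restarts and for several stops per patient, taking the first. Someone who paused early, restarted and had an on-treatment Week 12 LDL-C is in mITT and is counted.

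**Conclusion.** The point holds as a defect in a stated default. Followed as written, SAP 2.4.4.4 runs its tables on a set that excludes every permanent stop before Day 50. The discontinuation percentage and its breakdowns, and the summaries of very low values and statin changes in patients who stopped early, are then conditioned on staying on drug. The Day 50 limit is exact, given the Table 3 window and the 21-day rule.

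The size is not known. The documents assume no discontinuation rate for this study, so the fall from 10% to between 8.2% and 5.3% rests on assumed values of D and e and on complete Week 12 sampling otherwise.

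A reader might instead divide the first 49 days by planned follow-up: 49/84 = 58% at Week 12, down to 49/840 = 6% at Week 120. The documents do not support using this as the size. It needs a constant stopping rate and a known follow-up duration, and neither is given. It is also the share of stops lost, not the error in the reported percentage. Nor do the documents show that early stops are mainly allergic or intolerance-related.

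All analyses are descriptive and the primary safety analyses are unaffected, so the consequence is limited to how the 2.4.4.4 tables read.

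**What to change.** Add to SAP 2.4.4.4 that the discontinuation and statin tables use the safety population, and that the very-low-LDL-C tables, including later treatment changes, use safety-population patients with at least one post-baseline LDL-C.

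In the same place, define the observational period and say whether *discontinued* includes temporary stops. Cross-refer to SAP 2.2. Naming the population will not by itself reconcile the two discontinuation percentages: SAP 2.2 counts permanent stops over enrolled patients, while 2.4.4.4 allows for restarts. A footnote giving both definitions and denominators would do it.

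The cost is a few sentences and a rerun on an existing population flag. No new data are needed.

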#### ***Concomitant treatment with statins***

In order to assess the treatment with statins, the number and percentage of patients with statin dose decreased and statin discontinuation will be provided:

- Overall.
- In patients initiated on alirocumab 75 mg.
- In patients initiated on alirocumab 75 mg and who were up-titrated to 150 mg.
- In patients initiated on 150 mg.
- In patients with at least one value of LDL-C <25 mg/dL.

The 95% CI will be provided. In case of a number of patients deemed insufficient, the Clopper-Pearson algorithm will be used to compute the 95% CI.

#### **2.4.5 Analyses of safety data**

##### *General common rules*

All safety analyses will be performed on the Safety population using the following common rules:

- The baseline value will be defined as the last available value before the first alirocumab injection.
- The potentially clinically significant abnormality (PCSA) values are defined as abnormal values considered medically important by the Sponsor according to predefined criteria/thresholds based on literature review and defined by the Sponsor for clinical laboratory tests and vital signs (PCSA version dated May 2014, see [Appendix A](#)).
- PCSA criteria will determine which patients had at least 1 PCSA during the TEAE period, taking into account all evaluations performed during the TEAE period, including unscheduled or repeated evaluations. The number of all such patients will be the numerator for the PCSA percentages.

- The treatment-emergent PCSA denominator for a given parameter will be based on the number of patients assessed for that given parameter in the TEAE on the safety population.
- The worst on-treatment value is defined as the nadir and/or the peak value during the treatment period according to the direction (Min or Max) of the abnormality as defined the PCSA list. The last on-treatment value is defined as the last value collected during the treatment period.
- All measurements, scheduled or unscheduled, fasting or not fasting, will be assigned to analysis windows defined in [Section 2.5.4](#) in order to provide an assessment for all time points.

#### **2.4.5.1 Analyses of adverse events**

##### ***Generalities***

The primary focus of adverse event reporting will be on TEAEs. Pre-treatment adverse events will be described separately. Likewise, the post-treatment adverse events for the patients concerned (see [Section 2.1.4](#)) will also be described separately.

If an adverse event date/time of onset (occurrence, worsening, or becoming serious) is incomplete, an imputation algorithm will be used to classify the adverse event as pre-treatment or treatment-emergent. The algorithm for imputing date/time of onset will be conservative and will classify an adverse event as treatment emergent unless there is definitive information to determine it is pre-treatment. Details on classification of adverse events with missing or partial onset dates are provided in [Section 2.5.3](#).

Adverse event incidence tables will present by SOC internationally agreed order, HLT, HLT, and PT, sorted in alphabetical order, the number (n) and percentage (%) of patients experiencing an adverse event. Multiple occurrences of the same event in the same patient will be counted only once in the tables within a treatment phase.

For the TEAEs as well as for the pre-treatment adverse events, the denominator for computation of percentages is the safety population. Instead, for the post-treatment adverse events, the denominator will be a sub-group of the safety population (see [Section 2.1.4](#)).

Sorting within tables ensures the same presentation for the set of all adverse events within the observation period (pre-treatment, treatment-emergent, post-treatment). For that purpose, the table of all TEAEs presented by SOC and PT sorted by the internationally agreed SOC order and decreasing frequency of PTs within SOCs will define the presentation order for all other tables unless otherwise specified.

### ***Analysis of all treatment-emergent adverse events***

The following TEAEs summaries will be generated for the safety population.

- Overview of TEAEs, summarizing number (%) of patients with any
  - Treatment-emergent adverse event,
  - Serious TEAE,
  - Treatment-emergent adverse event leading to death,
  - Treatment-emergent adverse event leading to permanent treatment discontinuation.
- All TEAEs by primary SOC, HLT, HLT, and PT.
- All TEAEs by primary SOC, HLT, HLT, and PT, showing number (%) of patients with at least 1 TEAE sorted by the SOC internationally agreed order. The other levels (HLT, HLT, PT) will be presented in alphabetical order.
- All TEAEs by primary SOC and PT, showing the number (%) of patients with at least 1 TEAE by primary SOC and PT, sorted by the internationally agreed SOC order and by decreasing incidence of PTs within each SOC. This sorting order will be applied to all other tables, unless otherwise specified.
- All TEAEs by PT, showing the number (%) of patients with at least 1 TEAE, sorted by decreasing incidence of PTs.
- All TEAEs regardless of relationship (in one column of the table) and related to alirocumab according to investigator's opinion (in a second column) by primary SOC, HLT, HLT and PT, showing the number (%) of patients with at least 1 TEAE, sorted by the internationally agreed SOC order. The other levels (HLT, HLT, PT) will be presented in alphabetical order.
- All TEAEs by maximal severity, presented by primary SOC and PT, showing the number (%) of patients with at least 1 TEAE by severity (ie, mild, moderate, or severe), sorted by the sorting order defined above.
- The event rate per patient-year (the number of patients with an event in question divided by total patient-years) will be provided for all TEAEs by SOC and PT. For a patient with event, patient year is censored at time of first event; for patient without event, it corresponds to length of TEAE period.
- Kaplan-Meier curves will be provided, when appropriate, for time from first dose of alirocumab to the first occurrence of selected TEAEs as well as incidence rates at 24 weeks of exposure. Patients without any event will be censored at the end of the TEAE period. Selected TEAEs will be all AESIs (as defined in [Section 2.1.4.1](#)).

### ***Analysis of all treatment emergent serious adverse event(s)***

- All serious TEAEs by primary SOC, HLT, HLT, and PT.
- All treatment-emergent SAEs by primary SOC, HLT, HLT, and PT, showing the number (%) of patients with at least 1 serious TEAE, sorted by the internationally agreed SOC order. The other levels (HLT, HLT, PT) will be presented in alphabetical order.

- All treatment-emergent SAEs regardless of relationship (in one column of the table) and related to alirocumab according to investigator's opinion (in a second column), by primary SOC, HLGT, HLT, and PT, showing the number (%) of patients with at least 1 treatment-emergent SAE, sorted by the internationally agreed SOC order. The other levels (HLGT, HLT, PT) will be presented in alphabetical order.
- All treatment-emergent SAEs by PT, showing the number (%) of patients with at least 1 TEAE, sorted by decreasing incidence of PTs.
- The event rate per patient-year will be provided for all serious TEAEs by SOC and PT.

#### ***Analysis of all TEAEs leading to treatment discontinuation***

- All TEAEs leading to treatment discontinuation, by primary SOC, HLGT, HLT, and PT, showing the number (%) of patients sorted by the internationally agreed SOC order. The other levels (HLGT, HLT, and PT) will be presented in alphabetical order.

#### ***Analysis of adverse event of special interest (AESI)***

- All AESIs as listed in [Section 2.1.4.1](#) will be analyzed using selections defined in [Section 2.1.4.1](#) and will be presented by SOC and PT (indicating in the footnote if selection is based on SMQ or HLGT/HLT). The summaries will be sorted by decreasing incidence of PT within each SOC.

In addition, the following variables will be tabulated for the local injection site reactions TEAEs:

- Intensity of the event (mild, moderate, severe).
- Number of events divided by the number of alirocumab injections received.
- Time from first alirocumab injection to first injection site reaction.
- Description of the highest intensity of each symptom recorded in the specific eCRF page.

Besides, description of symptoms and possible etiologies for General Allergic Reaction TEAE reported by investigator will be listed (ie, presented by listing).

